7.2.5 Sponsor Responsibility for Reporting Adverse Events

All Adverse Events will be reported to regulatory authorities, IRB/IECs and investigators in accordance with all applicable global laws and regulations, i.e., per ICH Topic E6 (R1) Guidelines for Good Clinical Practice.

8.0 STATISTICAL ANALYSIS PLAN

8.1 Statistical Analysis Plan Summary

This section contains a brief summary of the statistical analyses for this trial. Full details can be found beginning in Section 8.2).

Statistical Methods

Safety:

Incidence of adverse experiences will be descriptively summarized. Summary statistics and plots will be generated for the change from baseline values in the vital signs, ECG parameters, and selected laboratory safety parameters for subjects, as deemed clinically appropriate. Depending on the safety parameter, the difference from baseline will either be computed on the original scale (raw change from baseline) or on the log scale and back-transformed for reporting (percent change from baseline). Summary statistics for the raw laboratory safety tests, ECGs, and/or vital signs may also be computed, as deemed clinically appropriate. Results will be summarized separately by study part.

Pharmacodynamics

Individual maximal GIR values (GIRmax) based on LOESS smoothed data will be analyzed in a linear mixed effects model with fixed effects for treatment (i.e. glargine, MK-5160 Dose Level 1, MK-5160 Dose Level 2, MK-5160 Dose Level 3), day (Day 1, Day 12) and treatment by day interaction, a continuous covariate for BMI, and a random effect for subject. A separate model will be used for each patient population (T1DM, T2DM).

GIRmax means and 95% confidence intervals for each treatment/day will be calculated from the model. To test the primary hypothesis, the posterior probability that the true mean GIRmax level at steady state is within 1.5 and 4.5 mg/kg/min will be calculated for each MK-5160 dose on Day 12 using a non-informative prior. If this posterior probability exceeds 70% for at least one safe and well tolerated dose of MK-5160 for each population, then the primary research hypothesis will be supported.

Between treatment GIRmax comparisons (MK-5160 versus glargine) will be performed for each dose of MK-5160 and on each day, using the model.

Pharmacokinetics

Non-compartmental Analysis (NCA) based geometric means and 95% confidence intervals will be provided for Cmax, AUC0-24hr, Css and CL by treatment, day and population. The geometric mean accumulation ratio (Day 12 PK / Day 1 PK) and 90% CI will be calculated for Cmax and AUC0-24hr.

Scatterplots of individual PK values (Steady state AUC0-24hr, Cmax, Css) versus BMI will be plotted for each patient population.

Individual values will be listed for each PK parameter by treatment and day and the additional following (NCA-based) descriptive statistics will be provided: N (number of subjects with non-missing data), arithmetic mean, standard deviation, arithmetic percent CV (calculated as 100 x standard deviation/ arithmetic mean), median, minimum, maximum, geometric mean, and geometric percent CV (calculated as 100 x sqrt(exp(s2) - 1), where s2 is the observed variance on the natural log-scale). For Tmax, only median, minimum and maximum will be calculated.

Pharmacokinetic endpoints following administration with glargine may be summarized in a similar fashion, as appropriate.

Power

Pharmacodynamics

This is the first study of MK-5160 in a diabetic patient population, and as such no variance estimates exist other than those from a single dose study in normal healthy volunteers (P001). In order to provide an approximate estimate of power, the variability observed in P001 has been used for the power calculations presented below (Table 8). [REDACTED]

Table 8 Probability of Supporting Primary PD Hypothesis

Target GIRmax (mg/kg/min)	True GIRmax	Probability of Supporting Hypothesis
(1.5, 4.5)	1	2%
	1.5	30%
	2	86%
	2.5	99%
	3	99%
	3.5	99%
	4	86%
	4.5	30%
	5	2%

The calculations above were based on [REDACTED] and N=6 per dose, and a posterior probability threshold of 70%.

8.2 Responsibility for Analyses

The statistical analysis of the data obtained from this study will be conducted by, or under the direct auspices of, the Clinical Pharmacology Statistics Department in collaboration with the Quantitative Pharmacology and Pharmacometrics (QP2), and Translational Pharmacology Departments of the Sponsor.

If, after the study has begun, changes are made to the statistical analysis plan stated below, then these deviations to the plan will be listed, along with an explanation as to why they occurred, in the Clinical Study Report.

8.3 Hypotheses/Estimation

Primary:

At a dose with sufficient safety, the mean steady-state maximum level of GIR (GIRmax) after MK-5160 administration in both T1 and T2 DM patients is between 1.5 and 4.5 mg/kg/min.

8.4 Analysis Endpoints

Primary:

Safety

The primary safety endpoints in this study will include all types of adverse experiences, in addition to laboratory safety assessments, ECGs, and vital signs.

Pharmacodynamics

The primary pharmacodynamic variable in this study is the glucose infusion rate (GIR) required to maintain plasma glucose at each subjects' individual clamp target, following administration of MK-5160 or glargine. To assess the primary hypothesis, individual maximal GIR (GIRmax) values at steady state (Day 12) will be used. Prior to obtaining the maximal GIR values, data will be smoothed (LOESS) to minimize variability and the potential impact of transient outliers influencing the estimation. The default smoothing function in SAS PROC LOESS, which selects an optimal smoothing parameter based on minimizing a bias corrected AIC criterion, will be used to fit an optimal smoothing function for each subject.

Additional clamp endpoints that may be analyzed in a similar fashion as above include GIR AUC endpoints over the entire clamp timeframe (0-24 hours) as well as various subfractions of interest (e.g. 0-12, 12-24 hours and 24-end for the Day 12 clamp), though these would be based on raw data and not LOESS smoothed.

Secondary:

Pharmacokinetics

The pharmacokinetic variables of interest include Cmax, Css, Steady State AUC0-24hr, CL, Tmax and t1/2 of MK-5160 after SC administration. Similar endpoints for glargine may also be of interest, as appropriate.

Exploratory:

Pharmacodynamics

The exploratory pharmacodynamic endpoints in this study include FFA, glycerol, triglycerides, β -hydroxybutyrate, glucagon and fasting morning glucose levels, following SC administration of MK-5160 or glargine. Baseline is the Day 1 Predose value.

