2.0 TRIAL DESIGN

2.1 Trial Design

This is a randomized, active- and placebo-controlled, parallel-group, single-site, double-blind trial of MK-5160 in subjects with type 1 and type 2 diabetes mellitus (DM).

This is a two-part trial, with three panels per part. Type 1 diabetes mellitus (Part 1) and Type 2 DM (Part 2) subjects will be given daily fixed doses of MK-5160 or glargine (active comparator) in three predefined, increasing doses in each panel. The first panel in Part 1 will be the initial panel; the second panel in Part 1 and first panel in Part 2 will be initiated after review of preliminary safety and pharmacodynamics from the initial panel. Different subjects will participate in each panel.

T2DM subjects in Part 2 may be on a single anti-hyperglycemic agent (AHA) of a permissible class (metformin, DPP4 inhibitor, sulfonylurea, or alpha-glucosidase inhibitors) **or** metformin in combination with one additional permissible AHA (a DPP4 inhibitor, sulfonylurea, or alpha-glucosidase inhibitor), at stable doses for at least 8 weeks prior to screening. Subjects may also be on insulin in addition to the above, or on insulin alone.

Subjects taking metformin and/or a DPP-4 inhibitor will continue these medications at their pre-enrollment doses throughout study participation, but subjects taking a sulfonylurea or an alpha-glucosidase inhibitor will discontinue the sulfonylurea or alpha-glucosidase inhibitor at screening, at least 7 days prior to CRU admission, and remain off until the completion of dosing.

All subjects would be brought into the site on Day -4, placed on continuous glucose monitoring (CGM), and started on an appropriate dose of fast-acting insulin, to be administered via a subcutaneous (SC) pump that will remain in place for the duration of dosing. The SC pump will be placed in all subjects during the washout period with the exception of non-insulin requiring T2DM subjects. Subjects will be domiciled for the entirety of MK-5160/glargine dosing, receiving standard meals and snacks. Prandial and (if needed) rescue insulin will be dosed throughout the trial according to standard clinical practice and at the discretion of the investigator, taking both the pre-prandial glucose level (fingerstick) and the carbohydrate content of the planned meal into account. In addition, subjects will have fingerstick glucose levels checked prior to bedtime and once overnight, and as needed per the subject and/or Investigator.

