On Day -1, the insulin via the SC pump will be discontinued, and subjects will be fasted overnight while also receiving insulin and dextrose via IV infusions, as needed, to set plasma glucose levels at 100 mg/dL prior to dosing and clamp initiation. On Day 1, subjects will be administered MK-5160 or glargine (3:1) SC. Subjects will be blinded in a double-dummy fashion, so that each subject will get two injections, one of which would be placebo. Subjects would continue to be on CGM, but will also be on a euglycemic clamp (fasted) for ~24 hours after this first dose. After completion of the euglycemic clamp, subjects will restart the standardized diet and continue to receive daily SC MK-5160/glargine at the same dose, with continued prandial insulin at the dosing discretion of the investigator via the SC pump. If necessary to treat hyperglycemia, subjects may also receive bolus and/or infused insulin via the SC pump, at the discretion of the Investigator.

On Day 7, subjects will not be given an evening meal or a pre-bedtime snack, while continuing to be domiciled and on CGM. A “pre-dinner” glucose measurement will be obtained, and hyperglycemia will be corrected if necessary, but subjects will then initiate a fast. By not taking the evening meal and snack on Day 7, subjects will be exposed to a fasting stress to assess the extent of nighttime hypoglycemia, while the subjects continue to be closely monitored. Hypoglycemia (and hyperglycemia), if observed, will be treated as outlined in Appendix 12.6, at the discretion of the Investigator according to the site’s standard operating procedures. If the individual subject does not require intervention for hypoglycemia after this Day 7 fast, a similar fasting will occur for that subject on Day 9. Subjects will have a normal meal schedule on Day 8, and on Days 10-11.

MK-5160 is expected to be at steady-state prior to Day 12. On the evening of Day 11, subjects will be fasted overnight on insulin and dextrose IV infusions, and then given MK-5160/glargine on a euglycemic clamp, as on Day 1. This clamp may continue beyond 24 hours, to assess duration of action. After completion of this clamp, subjects will restart the standardized diet but also restart their home insulin regimen. Subjects will be discharged from site ~48 hours after the final clamp, when glucose levels are stable.

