NCA based geometric means and 95% confidence intervals will be provided for Cmax, AUC0-24hr, Css and CL by treatment, day and population. The geometric mean accumulation ratio (Day 12 PK / Day 1 PK) and 90% CI will be calculated for Cmax and AUC0-24hr.

Scatterplots of individual PK values (Steady state AUC0-24hr, Cmax, Css) versus BMI will be plotted for each patient population.

Individual values will be listed for each PK parameter by treatment and day and the additional following (NCA-based) descriptive statistics will be provided: N (number of subjects with non-missing data), arithmetic mean, standard deviation, arithmetic percent CV (calculated as $100 \times \text{standard deviation}/\text{arithmetic mean}$), median, minimum, maximum, geometric mean, and geometric percent CV (calculated as $100 \times \text{sqrt}(\exp(s^2) - 1)$, where s^2 is the observed variance on the natural log-scale). For Tmax, only median, minimum and maximum will be calculated.

Pharmacokinetic endpoints following administration with glargine may be summarized in a similar fashion, as appropriate.

Exploratory

Pharmacodynamics

Plasma FFA, glycerol, triglycerides, β -hydroxybutyrate, glucagon and fasting morning glucose levels, following SC administration of MK-5160 or glargine will be summarized with descriptive statistics and plotted over time. More formal treatment comparisons (MK-5160 versus glargine) may also be performed. Baseline is the Day 1 Predose value.

Pharmacokinetics/Pharmacodynamics

Exploratory PK/PD plots linking PD measures (GIR, Glucose, FFA and other secondary PD measures) to PK measures (concentration at different timepoints, Cmax, steady state AUC0-24hr) may be plotted as deemed necessary. MK-5160 PK/PD relationship will be explored using an integrated PK/PD modeling approach as necessary.

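### The stated baseline for fasting morning glucose (Day 1 predose) is a value the protocol sets to 100 mg/dL by infusion, and the Day 2 and Day 12 mornings are also set by procedure

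*Combined protocol and SAP*

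**What the plan says.** Exploratory objective 2 (Section 3.3) is to explore fasting morning glucose on MK-5160 against glargine. Section 8.4 lists the endpoint with five other analytes under one baseline rule; the list closes with "glucagon and fasting morning glucose levels, following SC administration of MK-5160 or glargine. Baseline is the Day 1 Predose value". Section 8.6 says the levels will be summarized descriptively and plotted against time, then adds: "More formal treatment comparisons (MK-5160 versus glargine) may also be performed. Baseline is the Day 1 Predose value". No separate baseline is given for glucose.

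Section 2.1 describes what happens around three of the dosing mornings:

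- Before the Day 1 dose, subjects fast overnight while "receiving insulin and dextrose via IV infusions, as needed, to set plasma glucose levels at 100 mg/dL prior to dosing and clamp initiation".
- After that dose they stay on CGM "but will also be on a euglycemic clamp (fasted) for ~24 hours after this first dose".
- From the evening of Day 11 they are "fasted overnight on insulin and dextrose IV infusions, and then given MK-5160/glargine on a euglycemic clamp, as on Day 1".

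On the days between, subjects return to a standardized diet and a fixed daily study dose. Dinner and the evening snack are withheld on Day 7, and again on Day 9 for subjects who needed no intervention for hypoglycemia after the first fast.

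**The concern.** A baseline is useful when it records where the subject stood before treatment. For glucose, the Day 1 predose value mainly records how well the overnight infusions reached their target. Subtracting it says nothing about the subject's untreated or usual fasting glucose. The same problem affects the Day 2 and Day 12 mornings as outcome values, because infusions rather than the basal effect of the study drug largely determine them.

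At stake is the reading of one exploratory endpoint, which Section 3.3 describes as a secondary look at the drug's effect on glucose metabolism. A table of change from baseline, or a time plot in which Days 1, 2 and 12 look like ordinary fasting values, could be taken as evidence about basal effect when it carries almost none.

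**Working it through.** The plan gives no figure to reproduce here. The check sets the baseline rule beside the schedule.

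**Inputs**

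- Baseline: Day 1 predose (Sections 8.4 and 8.6).
- Predose glucose target on Day 1: 100 mg/dL (Section 2.1).
- Clamp target: 100 mg/dL (Sections 2.1 and 4.2.3.3, Table 3, flow chart).
- Dosing: every morning of Days 1-12 after a fast of at least 8 hours (Sections 5.2.2 and 7.1.5.2).
- Withheld dinners: Days 7 and 9 (Sections 2.1 and 5.7.1).

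**Step 1: classify the mornings**

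| Morning | What precedes it | Status |
|---|---|---|
| Day 1 | Overnight IV insulin and dextrose, as needed, to 100 mg/dL | Set by procedure; this is the baseline |
| Day 2 | About 24 hours of clamp, fasted throughout | Set by procedure |
| Days 3, 4, 5, 6, 7, 9, 11 | Ordinary night on standardized diet | Usable fasting value |
| Days 8, 10 | No dinner or evening snack | Usable, but after an extended fast |
| Day 12 | Overnight IV insulin and dextrose again | Set by procedure |

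Of 12 dosing mornings, 3 are set by procedure: 3/12 = 25%. Leaving out Day 1, which is the baseline and not an outcome, 11 mornings remain, of which 2 are affected: 2/11 = 18%. Usable mornings: 11 - 2 = 9, made up of 7 ordinary nights and 2 extended fasts. The Day 13 morning, if anyone tabulates it, also falls under the second clamp, which may run up to 30 hours.

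**Step 2: within-arm change**

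Let Y(d) be the fasting value on day d. The change is C(d) = Y(d) - Y(1), with Y(1) about 100.

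- Day 12: C(12) = 100 - 100 = about 0 mg/dL in every arm.
- Day 2: also about 0 while the clamp holds the target.
- Days 3-11: C(d) = Y(d) - 100. This is the observed level shifted by a near-constant, with no information on the subject's starting point.

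**Step 3: between-arm difference**

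On any of Days 3-11, (mean Y for MK-5160 - 100) - (mean Y for glargine - 100) = mean Y for MK-5160 - mean Y for glargine. The baseline cancels, so the comparison with glargine is not harmed by it. On Days 2 and 12 the baseline also cancels, but the levels themselves are held near 100 in both arms, so a difference near 0 there says nothing about the drugs.

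**Step 4: is a better reference already collected?**

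The flow chart schedules fingersticks from Day -4, and its footnote p places them before meals. Pre-breakfast values on Days -3 to -1 therefore precede the overnight infusions. Section 7.1.3.1 requires fasting for the Day -1 safety laboratory tests, and glucose is in that chemistry panel. Those tests may be drawn up to 30 hours before dosing, so their time relative to the start of the infusions needs checking.

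**The case against.** The strongest reply is that the SAP does not promise the analysis criticised. Section 8.6 commits to summarizing and plotting levels. Change from baseline is spelled out only for safety variables, and the baseline sentence is a general label for six analytes. Objective 2 is a comparison with glargine, for which a near-constant baseline cancels. All of that stands, and it means the documents do not support saying that the trial will report a fall in fasting glucose as a rise, or that the MK-5160 versus glargine comparison is biased. It does not rescue the baseline sentence. That sentence appears twice with fasting glucose among the endpoints it covers. If it is used for glucose, the result is uninformative; if it is not, it should not be there for glucose.

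A second reply is that the pre-treatment mornings are not clean either. Section 2.1 says: "The SC pump will be placed in all subjects during the washout period with the exception of non-insulin requiring T2DM subjects". Where a pump is used, change from those mornings contrasts pump insulin with the study drug and is not a pure drug effect. That stands, and the replacement text should say so.

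A third is that Section 7.1.5.2 ties the clamp target to the subject's own baseline fasting glucose, and Section 8.4 speaks of individual targets. Section 2.1 still puts the predose value at 100 mg/dL, and the value is taken after overnight infusions on either reading.

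A reader might go further and infer that corrective insulin hides a difference between arms on Days 3-11 by some calculable amount. Section 2.1 does allow it: "If necessary to treat hyperglycemia, subjects may also receive bolus and/or infused insulin via the SC pump, at the discretion of the Investigator". Objective 7, on non-basal insulin, has no endpoint in 8.4 and no method in 8.6. But the documents give neither how often corrections occur nor how much they lower glucose, so no size can be attached. Objective 7 is stated, and Section 7.1.1.5.2 has medication during the trial recorded. Its absence from Section 8 is missing detail, not an error.

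**Conclusion.** The point holds in a limited form. For fasting morning glucose, Day 1 predose is an uninformative reference because the protocol sets it, and the Day 2 and Day 12 mornings should not be read as ordinary fasting values. The clearest consequence is that Day 12 minus Day 1 is about 0 mg/dL in every arm regardless of drug effect. Two of the 11 mornings after the first dose are affected as outcomes; nine are not.

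This assumes that the infusions reach their target reasonably well. They are given as needed, and the investigator may end the clamp sooner or later than 24 hours, so the Day 2 value is held less firmly than the other two. Even then it follows a fast that began the evening before Day 1 and is not an ordinary overnight value.

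The harm falls on within-arm change and on displays that include Days 1, 2 and 12 unmarked. Raw between-arm comparisons on Days 3-11 and the primary GIRmax analysis are unaffected. Since the endpoint is exploratory and the SAP does not commit to change from baseline for it, this is a correction to consider, not a flaw in the trial.

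**What to change.** In Sections 8.4 and 8.6, for fasting morning glucose only:

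1. Replace the Day 1 predose baseline with a fasting value taken before the infusions: the pre-breakfast fingersticks of Days -3 to -1, or the fasting Day -1 chemistry glucose if it is drawn before the infusions start.
2. State that this baseline is on pump insulin where a pump is used, so that change from it contrasts two insulin regimens.
3. Base the MK-5160 versus glargine summary, and any formal comparison, on the mornings of Days 3-11. Flag Days 8 and 10 as following extended fasts (Day 10 only in subjects who did the second fast).
4. Exclude Days 2 and 12, or mark them in tables and plots as infusion-controlled.

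The other exploratory analytes can keep their present baseline as far as this point goes. Showing objective 7 insulin use beside the fasting glucose table would be a sensible addition for completeness.

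The cost is a slightly longer baseline definition and a reference measured on a different insulin background. It uses data already scheduled and needs no new visits, samples or subjects.

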8.5 Analysis Populations

The following populations are defined for the analysis and reporting of data. All subjects will be reported, and their data analyzed, according to the treatment(s) they actually received.

All Subjects as Treated (AST) – All subjects who received at least one dose of the investigational drug. This population will be used for assessments of safety and tolerability.

Per-Protocol (PP) – The set of data generated by the subset of subjects who comply with the protocol sufficiently to ensure that these data will be likely to exhibit the effects of treatment, according to the underlying scientific model. Compliance covers such considerations as exposure to treatment, availability of measurements and absence of major protocol deviations. Major protocol deviators will be identified to the extent possible prior to unblinding by individuals responsible for data collection/compliance, and its analysis and interpretation. Any subjects or data values excluded from analysis will be identified, along with their reason for exclusion, in the CSR. At the end of the study, all subjects who are compliant with the study procedure as aforementioned and have available data from at least one treatment will be included in the primary analysis dataset. This population will be used for the PK and PD analyses.

